Vital signs (oral temperature, pulse and blood pressure [BP]) will be collected at the screening visit (optional) and prior to study vaccination. Vital signs may be obtained if indicated at approximately 1, 3 and 7 days after study vaccination (this may only occur approximately 7 days after study vaccination for sites not processing blood for PBMCs isolation). Vital signs assessed on Day 1 prior to study vaccination will be considered as baseline. Subjects must not eat or drink anything hot or cold, or smoke within 10 minutes prior to taking oral temperature.

Height and weight will be collected at the screening visit (optional) or on Day 1 prior to study vaccination for the calculation of BMI.

Reactogenicity assessments will include an assessment of solicited AEs occurring from the time of study vaccination through 7 days after study vaccination, which includes an assessment of

injection site reactions including pruritus, ecchymosis, erythema, induration, edema, pain, and tenderness as well as systemic reactions including fever, feverishness, fatigue, malaise, myalgia, arthralgia, headache, and nausea. Pre-administration reactogenicity assessments will be performed immediately prior to study vaccination to establish baseline, then the study vaccination will be given.

Subjects will be observed in the clinic for at least 20 minutes after study vaccination. The study vaccination site will be examined, post-administration reactogenicity assessments will be performed, and any AE/SAEs will be recorded on the appropriate DCF prior to discharge from the clinic. The study vaccination site will also be examined approximately 1, 3 and 7 days after study vaccination (this will only occur approximately 7 days after study vaccination for sites not processing blood for PBMCs isolation).

All subjects will complete a Memory Aid from the time of study vaccination through 7 days after study vaccination. Memory Aids will be reviewed with the subjects for any AEs (solicited injection site and systemic reactions as well as unsolicited AEs), SAEs and concomitant medications (including solicitation for receipt of any non-study influenza vaccines) approximately 1, 3 and 7 days after study vaccination via phone call or clinic visit.

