8.2 Follow-up Visits

Follow-up visits are scheduled in reference to study vaccination dates as indicated for each visit window.

8.2.1 Visit 02, Day 2, Clinic Visit (Window: Day 2+1 day post study vaccination)

- Interim medical history, including an assessment for new medical conditions, stability of chronic diseases and symptoms suggestive of PIMMCs, will be obtained by interview of subjects and any changes since the previous clinic visit or phone call will be noted.
- Concomitant medications (including solicitation for receipt of any non-study influenza vaccines) will be recorded on the appropriate DCF.
- All AE/SAEs will be recorded on the appropriate DCF.

- Memory Aid information will be reviewed with subjects.
- Vital signs, including oral temperature, pulse and BP, may be obtained if indicated. Subjects must not eat or drink anything hot or cold, or smoke within 10 minutes prior to taking oral temperature.
- A targeted physical examination, including an assessment for signs suggestive of PIMMCs, may be performed, if indicated based on review of interim medical history, by a study clinician licensed to make medical diagnoses and listed on the Form FDA 1572 as the site PI or sub-investigator.
- The study vaccination site will be examined.
- At sites processing blood for PBMCs isolation, approximately 16 mL of venous blood will be collected for future research.

Note: This visit may be performed as a phone call assessment for sites not processing blood for PBMCs isolation. Study personnel will contact these subjects by phone to review their Memory Aid information and solicit any AE/SAEs and concomitant medications (including solicitation for receipt of any non-study influenza vaccines). Based on the information collected, subjects may be asked to return to the clinic for evaluation.

8.2.2 Visit 03, Day 4, Clinic Visit (Window: Day 4+1 day post study vaccination)

- Interim medical history, including an assessment for new medical conditions, stability of chronic diseases and symptoms suggestive of PIMMCs, will be obtained by interview of subjects and any changes since the previous clinic visit or phone call will be noted.
- Concomitant medications (including solicitation for receipt of any non-study influenza vaccines) will be recorded on the appropriate DCF.
- All AE/SAEs will be recorded on the appropriate DCF.
- Memory Aid information will be reviewed with subjects.

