##### **4.5.1. Safety Variables**

Safety will be assessed by the frequency and severity:

1. SAEs occurring from the time of study vaccination through approximately 12 months after study vaccination.
2. Solicited AEs – reactogenicity events occurring from the time of study vaccination through 7 days after study vaccination:
  - a. Injection site reactions including pruritus, ecchymosis, erythema, induration/edema, pain, and tenderness.
  - b. Systemic reactions including fever, feverishness, fatigue, malaise, myalgia, arthralgia, headache, and nausea.
3. Clinical safety laboratory AEs occurring from the time of study vaccination through approximately 7 days after study vaccination. Parameters to be evaluated include white blood cell (WBC) count, hemoglobin (Hgb), platelets (PLT), alanine aminotransferase (ALT), total bilirubin (Bili), and creatinine (Cr).
4. Vital sign AEs occurring from the time of study vaccination through approximately 7 days after study vaccination. Parameters to be evaluated include pulse, systolic and diastolic blood pressures, and oral temperature.
5. Unsolicited AEs – non-serious AEs occurring from the time of study vaccination through approximately 21 days after study vaccination.
6. MAAEs, including NOCMCs and PIMMCs, occurring from the time of study vaccination through approximately 12 months after study vaccination.

Grading scales for injection site and systemic solicited reactions, vital signs, and clinical laboratory parameters are provided in [Table 9](#), [Table 10](#), [Table 11](#), and [Table 12](#).

For each unsolicited AE experienced, the subject will be asked if he/she had received medical attention, defined as hospitalization, an emergency room visit or an otherwise unscheduled visit to or from medical personnel for any reason. AEs characterized by such unscheduled medical care will be designated as MAAEs.

NOCMCs are defined as any new ICD-10 diagnosis (10th revision of the International Statistical Classification of Diseases and Related Health Problems) that is applied to the subject during the course of the study, after receipt of the study agent, that is expected to continue for at least 3 months and requires continued health care intervention.

PIMMCs constitute a group of AEs that includes diseases which are clearly autoimmune in etiology and other inflammatory and/or neurologic disorders which may or may not have autoimmune etiologies. For a list of PIMMCs currently in effect, refer to protocol Appendix B.

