## 6. GENERAL STATISTICAL CONSIDERATIONS

### 6.1. General Principles

All continuous variables will be summarized using the following descriptive statistics: n (non-missing sample size), mean, standard deviation, median, maximum and minimum. The frequency and percentages (based on the non-missing sample size) of observed levels will be reported for all categorical measures. In general, all data will be listed, sorted by study group and subject, and when appropriate by visit number within subject. All summary tables will be structured with a column for each Study Group in the following order:

- Group 1: 1 or 2 doses 2013 A/H7N9 + MF59 | 2017 A/H7N9 IIV 3.75mcg + AS03
- Group 2: 1 or 2 doses 2013 A/H7N9 + MF59 | 2017 A/H7N9 IIV 3.75mcg
- Group 3: 1 or 2 doses 2013 A/H7N9 + AS03 | 2017 A/H7N9 IIV 3.75mcg + AS03
- Group 4: 1 or 2 doses 2013 A/H7N9 + AS03 | 2017 A/H7N9 IIV 3.75mcg
- Group 5: 1 or 2 doses 2013 A/H7N9 15mcg or 45mcg | 2017 A/H7N9 IIV 3.75mcg + AS03
- Group 6: 1 or 2 doses 2013 A/H7N9 15mcg or 45mcg | 2017 A/H7N9 IIV 3.75mcg
- Group 7: 2013 A/H7N9 + MF59 or AS03 then 2013 A/H7N9 15mcg | 2017 A/H7N9 3.75mcg + AS03
- Group 8: 2013 A/H7N9 + MF59 or AS03 then 2013 A/H7N9 15mcg | 2017 A/H7N9 3.75mcg
- Group 9: A/H7N9 IIV-Naïve | 2017 A/H7N9 3.75mcg + AS03
- Group 10: A/H7N9 IIV-Naïve | 2017 A/H7N9 3.75mcg

All tables will be annotated with the total population size relevant to that table/arm, including any missing observations.

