## 9. SAFETY EVALUATION

All summaries and analysis of safety data will be presented for the safety population. Safety summaries will be presented overall and grouped by study group and stratum.

Continuous variables will be summarized using the following descriptive statistics: n (non-missing sample size), mean, standard deviation, median, maximum and minimum. All categorical measures will be summarized by the frequency and percentages of observed levels. The denominator for the percentages may be based on the number of non-missing observations for an assessment or based on the number of subjects in a population. This will be described for each table.

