## 9.7. Vital Signs and Physical Evaluations

Oral temperature, systolic blood pressure, diastolic blood pressure, and pulse will be assessed prior to study vaccination on Day 1 and these results will be considered as baseline. Additional measurements of vital signs may be taken on Day 2, Day 4, and Day 8 if indicated. The grading scale for vital sign evaluations is presented in [Table 11](#). Summaries of vital signs by maximum severity will be tabulated for baseline and post-baseline measurements, grouped by stratum and study group and presented in [Table 80](#), [Table 81](#), [Table 82](#), [Table 83](#), and [Table 84](#). A listing of vital signs will be presented in [Listing 16](#).

Targeted physical examinations will be performed, if indicated, based on a subject's medical history. A listing of physical exam findings will be presented in [Listing 17](#).

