Unrelated	x	x	x	x	x	x	x	x	x	x	x	x
At least one serious adverse event b	x	x	x	x	x	x	x	x	x	x	x	x
At least one related, serious adverse event	x	x	x	x	x	x	x	x	x	x	x	x
At least one adverse event leading to early termination c	x	x	x	x	x	x	x	x	x	x	x	x
At least one medically attended adverse event	x	x	x	x	x	x	x	x	x	x	x	x
At least one new onset chronic medical condition	x	x	x	x	x	x	x	x	x	x	x	x
At least one potentially immune mediated medical condition	x	x	x	x	x	x	x	x	x	x	x	x
At least one clinical safety laboratory adverse event	x	x	x	x	x	x	x	x	x	x	x	x
Mild (Grade 1)	x	x	x	x	x	x	x	x	x	x	x	x
Moderate (Grade 2)	x	x	x	x	x	x	x	x	x	x	x	x

	2013 A/H7N9 IIV + MF59 (N=X)		2013 A/H7N9 IIV + AS03 (N=X)		2013 A/H7N9 IIV 15 mcg or 45 mcg unadjuvanted (N=X)		2013 A/H7N9 IIV with MF59/AS03 then 2013 A/H7N9 IIV 15 mcg (N=X)		A/H7 IIV Naïve (N=X)		All Subjects (N=X)	
Severe (Grade 3)	x	x	x	x	x	x	x	x	x	x	x	x
At least one vital signs adverse event	x	x	x	x	x	x	x	x	x	x	x	x
Mild (Grade 1)	x	x	x	x	x	x	x	x	x	x	x	x
Moderate (Grade 2)	x	x	x	x	x	x	x	x	x	x	x	x
Severe (Grade 3)	x	x	x	x	x	x	x	x	x	x	x	x

Notes: N = Number of subjects in the safety population who received study vaccination in the given stratum; N* = Number of subjects in the safety population in the given study group; n = number of subjects with available results.
 
a Subjects are counted once for each category regardless of the number of events.
 
b A listing of Serious Adverse Events is included in Table 59
 
c As reported on the Adverse Event eCRF
												

**Table 49: Adverse Events Occurring in at least 5% of Subjects in Any Study Group by MedDRA System Organ Class and Preferred Term, Stratum and Study Group, Safety Population**

Preferred Term	MedDRA System Organ Class	2013 A/H7N9 IIV + MF59 (N=X)			2013 A/H7N9 IIV + AS03 (N=X)			2013 A/H7N9 IIV 15 mcg or 45 mcg unadjuvanted (N=X)			2013 A/H7N9 IIV with MF59/AS03 then 2013 A/H7N9 IIV 15 mcg (N=X)			A/H7 IIV Naïve (N=X)			2013 A/H7N9 IIV + MF59 (N=X)		
		n	%	Events	n	%	Events	n	%	Events	n	%	Events	n	%	Events	n	%	Events
3.75 mcg A/H7N9 IIV (N*=X)																			
Serious Adverse Events																			
All	All	x	x	x	x	x	x	x	x	x	x	x	x	x	x	x	x	x	x
PT1	SOC1	x	x	x	x	x	x	x	x	x	x	x	x	x	x	x	x	x	x
Etc.	Etc.																		
Other (Non-serious) Adverse Events																			
All	All	x	x	x	x	x	x	x	x	x	x	x	x	x	x	x	x	x	x
PT1	SOC1	x	x	x	x	x	x	x	x	x	x	x	x	x	x	x	x	x	x
Etc.	Etc.																		

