**14.3.6 Displays of Vital Signs**

**Table 80: Vital Signs by Assessment, Maximum Severity, Study Day, Stratum and Study Group – Any Assessment, Safety Population**

Study Group	Stratum	Study Day	N	None		Mild		Moderate		Severe		Missing	
				n	%	n	%	n	%	n	%	n	%
3.75 mcg A/H7N9 IIV	2013 A/H7N9 IIV + MF59	Baseline	X	x	xx	x	xx	x	xx	x	xx	x	xx
		Max Severity Post Baseline											
	2013 A/H7N9 IIV + AS03	Baseline											
		Max Severity Post Baseline											
	2013 A/H7N9 IIV 15 mcg or 45 mcg unadjuvanted	Baseline											
		Max Severity Post Baseline											
	2013 A/H7N9 IIV with MF59/AS03 then 2013 A/H7N9 IIV 15 mcg	Baseline											
		Max Severity Post Baseline											
	A/H7 IIV-Naive	Baseline											
		Max Severity Post Baseline											
	All Subjects	Baseline											
		Max Severity Post Baseline											

[repeat for 3.75 mcg A/H7N9 IIV + AS03 and All Subjects]

Note: N = Number of subjects in the safety population within the given study group and stratum with visit documentation for the corresponding day. The “Max Post Baseline” rows indicate the maximum severity experienced by each subject at any time point post baseline, including unscheduled assessments.

Table with similar format:

**Table 81: Vital Signs by Assessment, Maximum Severity, Study Day, Stratum and Study Group - Oral Temperature, Safety Population**

**Table 82: Vital Signs by Assessment, Maximum Severity, Study Day, Stratum and Study Group – Systolic Blood Pressure, Safety Population**

Study Group	Stratum	Study Day	N	None		Mild (Low)		Mild (High)		Moderate (Low)		Moderate (High)		Severe (Low)		Severe (High)		Missing	
				n	%	n	%	n	%	n	%	n	%	n	%	n	%	n	%
3.75 mcg A/H7N9 IIV	2013 A/H7N9 IIV + MF59	Baseline	x	x	xx	x	xx	x	xx	x	xx	x	xx	x	xx	x	xx	x	xx
		Max Severity Post Baseline																	
	2013 A/H7N9 IIV + AS03	Baseline																	
		Max Severity Post Baseline																	
	2013 A/H7N9 IIV 15 mcg or 45 mcg unadjuvanted	Baseline																	
		Max Severity Post Baseline																	
	2013 A/H7N9 IIV with MF59/AS03 then 2013 A/H7N9 IIV 15 mcg	Baseline																	
		Max Severity Post Baseline																	
	A/H7 IIV-Naive	Baseline																	
		Max Severity Post Baseline																	
	All Subjects	Baseline																	
		Max Severity Post Baseline																	
[repeat for 3.75 mcg A/H7N9 IIV + AS03 and All Subjects]																			

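### Topline Table 48 shows vital-sign AEs, which depend on measurements taken only if indicated, for the AS03 panel alone and with no stated denominator

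*SAP*

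**What the plan says.** **Measurement.** Baseline vital signs are taken in everyone before vaccination. Afterwards, Protocol 7.1 states: "Vital signs may be obtained if indicated at approximately 1, 3 and 7 days after study vaccination". SAP 9.7 agrees: "Additional measurements of vital signs may be taken on Day 2, Day 4, and Day 8 if indicated". For Day 2 and Day 4, Protocol 8.2 adds: "This visit may be performed as a phone call assessment for sites not processing blood for PBMCs isolation". Day 8 is a clinic visit at every site, but vital signs remain conditional there too.

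**Variable.** SAP 4.5.1 makes the frequency and severity of vital-sign AEs a safety variable, covering pulse, systolic and diastolic pressure and oral temperature: "Vital sign AEs occurring from the time of study vaccination through approximately 7 days after study vaccination".

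**Denominators.** SAP 6.1 sets a general rule: "The frequency and percentages (based on the non-missing sample size) of observed levels will be reported for all categorical measures". SAP 9 then allows either non-missing observations or the whole population in safety tables, and promises: "This will be described for each table".

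**Shells.** In Table 48 the unadjuvanted panel ends with the laboratory AE rows. The AS03 panel goes on to "At least one vital signs adverse event", split by grade. Table 49 has a vital-signs section in both arm panels but none under All Subjects. In Tables 80 to 84, N is "Number of subjects in the safety population within the given study group and stratum with visit documentation for the corresponding day", both arms appear, and there is a Missing column. Table 48 is starred as topline; under SAP 6.2.1 such tables are final analyses and may go to the lead investigator for publication.

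**The concern.** An event found by measurement can be counted only in someone who was measured. When measurement is optional and prompted by a clinical reason, a subject with no reading is not known to be event-free. Dividing by all vaccinated subjects treats that subject as event-free.

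The prompt may differ by arm. Protocol 2.3.1 reports higher rates of solicited injection-site and systemic events with AS03 than with antigen alone. If staff check pulse and pressure mainly in subjects with symptoms, more AS03 recipients could be checked, and more graded values found, without any effect of AS03 on vital signs.

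Table 48 makes this harder to see. Read alone, it would give a vital-sign AE rate for one randomised arm, with no matching row for the other and no count of subjects measured. The stake is modest: a misleading line in the main adverse-event summary of a descriptive trial.

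**Working it through.** **1. Is there a plan figure to reproduce?** No. Neither document gives an expected vital-sign AE rate or the fraction of subjects to be measured. The only planning input used below is 210 subjects per arm (SAP section 5: 210 receive adjuvant out of 420, allocated 1:1).

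**2. The shells side by side.**

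| Shell | Unadjuvanted | AS03 | All Subjects panel | Denominator |
|---|---|---|---|---|
| Table 48 | vital-sign rows absent | present | no such panel | N = all vaccinated in the stratum; basis of % not stated; n defined as subjects with results, although the rows count subjects with events |
| Table 49 | present | present | absent | N = safety population; n = subjects with the event; basis of % not stated |
| Tables 80–84 | present | present | present | subjects with a documented visit; Missing column |

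Table 48 is therefore the only one that drops an arm. It also does not state the denominator that SAP 9 says each table will describe.

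**3. How large could a measurement artefact be?** Let p be the true rate, the same in both arms, and m the fraction measured. If measurement is unrelated to the event within an arm:

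observed rate over N = p × m.

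The values of p and m are assumptions. The unadjuvanted fraction is set at 10%.

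| p | AS03 measured | AS03 over N | Unadjuvanted over N | Gap (points) | Approx. chance of two-sided p<0.05, 210 per arm |
|---|---|---|---|---|---|
| 5% | 20% | 1.0% | 0.5% | 0.5 | 9% |
| 5% | 40% | 2.0% | 0.5% | 1.5 | 28% |
| 10% | 20% | 2.0% | 1.0% | 1.0 | 13% |
| 10% | 30% | 3.0% | 1.0% | 2.0 | 31% |
| 10% | 40% | 4.0% | 1.0% | 3.0 | 50% |
| 20% | 20% | 4.0% | 2.0% | 2.0 | 22% |
| 20% | 40% | 8.0% | 2.0% | 6.0 | 81% |

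Example: 0.10 × 0.20 = 2.0% and 0.10 × 0.10 = 1.0%. The last column only gives a sense of scale, since neither document plans a test on this row. With equal fractions, such as 20% in each arm, the gap is 0 at every p. A real 20% against 10% would then show as 4% against 2% over N, keeping the ratio and shrinking the difference.

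**4. Would dividing by measured subjects cure it?** Assume 60% (AS03) and 30% (unadjuvanted) have symptoms, that 40% of symptomatic and 2% of other subjects are measured, and that the AE rate is 20% with symptoms and 5% without.

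| | AS03 | Unadjuvanted |
|---|---|---|
| True rate | 0.6×0.20 + 0.4×0.05 = 14.0% | 0.3×0.20 + 0.7×0.05 = 9.5% |
| Measured | 0.6×0.40 + 0.4×0.02 = 24.8% | 0.3×0.40 + 0.7×0.02 = 13.4% |
| Events found, over N | 0.6×0.40×0.20 + 0.4×0.02×0.05 = 4.8% | 0.3×0.40×0.20 + 0.7×0.02×0.05 = 2.5% |
| Events found, over measured | 0.0484/0.248 = 19.5% | 0.0247/0.134 = 18.4% |

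The true ratio is 14.0/9.5 = 1.47. Over N it becomes 0.0484/0.0247 = 1.96, and over measured 19.5/18.4 = 1.06. The first exaggerates the ratio and the second nearly removes a real difference. Neither recovers the truth.

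**The case against.** The strongest reply is that this is a slip in one shell and that the plan holds enough to correct it. Much of that stands, and it rules out four stronger readings that a reader might infer.

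- *That any arm difference merely reflects who was measured.* The documents do not support this. Allocation is randomised and stratified by site, staff assessing subjects after vaccination are blinded (Protocol 5.2.2, SAP 4.4.6), and equal measurement gives no spurious gap. Blinding does not remove a symptom-driven prompt, so a bias remains possible, but it is not established.
- *That vital-sign rates are divided by all subjects throughout.* SAP 6.1 specifies non-missing data, and Tables 80 to 84 use documented visits with a Missing column, from which the number measured can be derived. Tables 48 and 49 define N as the safety population without stating the basis of the percentage.
- *That no comparator exists.* Table 49 and Tables 80 to 84 show both arms, and Listing 16 gives every assessment.
- *That a measured-only denominator solves the problem.* Step 4 shows that it does not.

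Two further points stand. Oral temperature is also recorded daily by all subjects on the Memory Aid (Protocol 8.1.2 and 8.1.3), so the issue is mainly pulse and blood pressure. And although Protocol 9.1 does not list vital-sign AEs among its safety parameters, Protocol 9.2.3 does grade pulse and blood pressure as AEs, so the grading is not a SAP invention.

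**Conclusion.** The point holds as a small correction to reporting. Three things rest on the text alone: post-vaccination clinic vital signs are conditional; Table 48 shows the vital-sign rows for one arm only; and its footnote gives N as all vaccinated subjects, misdefines n and leaves the percentage undefined. The omission from the All Subjects panel of Table 49 is also plain.

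That the arms will be measured at different rates is an inference from the expected reactogenicity of AS03, not something the documents state. With 20–40% against 10% measured and equal true rates of 5–20%, the artefact over all vaccinated subjects is 0.5 to 6.0 points. It vanishes if measurement is balanced. No primary endpoint is affected.

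**What to change.** 1. Add the vital-sign AE rows, with grades, to the unadjuvanted panel of Table 48, and a vital-signs section to the All Subjects panel of Table 49.
2. In Table 48, redefine n as subjects with the event, and state the denominator of the percentage in the footnote.
3. Beside the vital-sign row, show by arm the number of subjects with at least one post-vaccination measurement.
4. Add a footnote that post-baseline vital-sign AEs are descriptive and not for comparing arms, because measurements were taken only if indicated and so may follow symptoms. If a rate among measured subjects is shown as well, do not present it as removing the selection.

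Tables 80 to 84 can keep their layout. The cost is shell and footnote edits plus one count from data already due for Listing 16. No change to data collection or visit procedures is needed.
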